**Sensitivity analyses:**

**Sensitivity analysis 1:** Analysis of time to metastasis will be conducted using only the appearance of documented metastases as event. In particular, deaths are not counted as events. Patients who died before documented metastasis will be censored. See Table 3 below with this change.

**Table 3: Censoring Rules**

Situation	End Date on or prior to cut-off date	Censored
Documented metastasis	Date of documented metastasis	No
Documented metastasis at baseline	Date of randomization	No CCI ██████████ ██████████
Documented metastasis after two or more consecutively missed tumor assessments, i.e. metastasis later than last evaluable scan + (32 +1) weeks	Date of last tumor assessment that the patient was known to be metastasis-free	Yes
Death before documented metastasis	Date of last tumor assessment that the patient was known to be metastasis-free	Yes
Discontinued the study before any post-baseline tumor assessment	Date of randomization	Yes
Discontinued the study with at least one post-baseline tumor assessment and no documented metastasis	Date of last tumor assessment before discontinuation	Yes
Prohibited new anticancer treatment started prior to documented metastasis	Date of last tumor assessment before start of prohibited new treatment	Yes
Patients still on treatment without documented metastasis as of data cut-off	Date of last tumor assessment	Yes

This endpoint is selected from the ADTTE dataset using variable PARAMCD equal to ‘SAMFS1’ (baseline metastasis non-censored) and ‘SAMFS2’ (baseline metastasis censored).

**Sensitivity analysis 2:** Analysis of MFS will be conducted with all prohibited new treatment started prior to documented metastasis considered as an event. See Table 4 below with this change.

**Table 4: Censoring Rules**

Situation	End Date on or prior to cut-off date	Censored
-----------	--------------------------------------	----------

Situation	End Date on or prior to cut-off date	Censored
Documented metastasis	Date of documented metastasis	No
Documented metastasis at baseline	Date of randomization	No CCI ██████████ ██████████
Documented metastasis after two or more consecutively missed tumor assessments, i.e. metastasis later than last evaluable scan + (32 +1) weeks	Date of last tumor assessment that the patient was known to be metastasis-free	Yes
Death before documented metastasis and not later than last evaluable scan + (32+1) weeks	Date of death	No
Death before documented metastasis and after two or more consecutively missed tumor assessments, i.e. death later than last evaluable scan + (32+1) weeks	Date of last tumor assessment that the patient was known to be metastasis-free	Yes
Discontinued the study before the post-baseline tumor assessments	Date of randomization	Yes
Discontinued the study before the post-baseline tumor assessments but died later than (32+1) weeks after randomization	Date of randomization	Yes
Discontinued the study before the post-baseline tumor assessments but died within (32+1) weeks after randomization	Date of death	No
Discontinued the study, but no documented metastasis	Date of last tumor assessment before discontinuation	Yes
Prohibited new anticancer treatment started prior to documented metastasis	Date of start of prohibited new treatment	No
Patients still on treatment without documented metastasis as of data cut-off	Date of last tumor assessment	Yes

This endpoint is selected from the ADTTE dataset using variable PARAMCD equal to ‘SAMFSPT1’ (baseline metastasis non-censored) and ‘SAMFSPT2’ (baseline metastasis censored).

If the complete date of the prohibited treatment is not known, but the year and month are available, Day 15 of the month will be used for the calculation.

**Sensitivity analysis 3:** similar analysis to the one created for the primary analysis for MFS with a two-sided model stratified by the stratification data from CRF. This endpoint is selected from the ADTTE dataset using variable PARAMCD equal to 'MFS' (baseline metastasis non-censored) and 'SAMFSBAS' (baseline metastasis censored).

**Sensitivity analysis 4:** similar analysis to the one created for the primary analysis for MFS with a two-sided log rank test without including stratification factors in the model. This endpoint is selected from the ADTTE dataset using variable PARAMCD equal to 'MFS' (baseline metastasis non-censored) and 'SAMFSBAS' (baseline metastasis censored).

**Sensitivity analysis 5:** similar analysis to the one created for the primary analysis for MFS, but using investigator assessment of radiological imaging. This endpoint is selected from the ADTTE dataset using variable PARAMCD equal to 'SAMFSIA1' (baseline metastasis non-censored) and 'SAMFSIA2' (baseline metastasis censored).

**Sensitivity analysis 6:** similar analysis to the one created for the primary analysis for MFS with all deaths independent when it occurred considered as an event. This endpoint is selected from the ADTTE dataset using variable PARAMCD equal to 'SAMFSDH1' (baseline metastasis non-censored) and 'SAMFSDH2' (baseline metastasis censored).

**Sensitivity analysis 7:** similar analysis to the one created for the primary analysis for MFS with event at date of first post baseline scan with metastasis instead of event at randomization for patients with baseline metastasis. If no metastasis documented in post baseline scans such patient will be censored at last available scan date. In case such a patient did not have any post baseline scan, the patient will be censored at randomization. This endpoint is selected from the ADTTE dataset using variable PARAMCD equal to SAMFSPB1' (baseline metastasis non-censored) and 'SAMFSPB2' (baseline metastasis censored).

Discordance of metastasis between independent blinded central reading and investigator assessment will be displayed.

Summary of baseline metastasis per independent blinded central reading and per charter version will be created.

Summary of eligibility read and efficacy read per charter version will be displayed.

Summary of adjudication reading will also be displayed.

The following flags will be available in the central imaging related datasets providing more detailed information on some specificities of the central reading process and versions of the imaging charter:

- Flags for charter version (flag\_ch1, flag\_ch2, flag\_ch3),
- Flags for adjudication (flag\_ad1, flag\_ad2, flag\_ad3),
- Flags for discordances between reviewers sets: eligibility, efficacy and confirmation of metastasis (flag\_dc, flag\_dc1, flag\_dc2),
- Flags for change of metastasis determination after final read (flag\_fb1, flag\_fb2).

Description	Value	Flag name
Charter version flag for eligibility (Charter cut-off 01 FEB 2017)	• v1.0 • v4.0	flag_ch1
Eligibility review adjudication 0 = no adjudication 1 = adjudication	• 0 • 1	flag_ad1
Charter version flag for confirmation of metastasis review	• v1.0	flag_ch2
Confirmation of Metastasis adjudication 0 = no adjudication 1 = adjudication	• 0 • 1	flag_ad2
Charter version flag for efficacy	v4.0	flag_ch3
Independent Efficacy Review Adjudication 0 = no adjudication 1 = adjudication	• 0 • 1	flag_ad3
Change of baseline response per Independent Efficacy Review triggered at final visit evaluation 0 = no change 1 = change from no metastasis to metastasis 2 = change from metastasis to no metastasis	• 0 • 1 • 2	flag_fb1
Change of metastasis progression per Independent Efficacy Review triggered at final visit evaluation 0 = no change 1 = change	• 0 • 1	flag_fb2
Metastasis at baseline per efficacy review 0 = no metastasis 1 = metastasis	• 0 • 1	flag_dc
Discordance of metastasis at baseline (Eligibility Review vs. Independent Efficacy Review) 0 = same result 1 = different results	• 0 • 1	flag_dc1
Comparison of confirmation of metastasis under Charter v1.0 where metastasis confirmed to the same time point as efficacy. 0 = same result 1 = different results	• 0 • 1	flag_dc2
Initial date of metastasis per before final visit evaluation (can be missing if no metastasis seen)	DDM MMY YYY	IMETSDT
Final date of metastasis per independent efficacy review before final visit evaluation (can be missing if no metastasis seen)	DDM MMY YYY	FMETSDT

### 6.2.2 Analysis of secondary efficacy endpoints

Secondary endpoints will be tested with the hierarchical gatekeeping procedure. The order of secondary endpoints is

- (1) Overall survival (OS),
- (2) Time to pain progression (PP),
- (3) Time to cytotoxic chemotherapy (CYTOC),
- (4) Time to first symptomatic skeletal event (SSE).

Secondary endpoints are tested only if the primary endpoint MFS is significant. They will be tested according to the sequence given above. If significance of the primary analysis of MFS is considered unmet, each of the secondary objectives will be considered unmet. The same overall two-sided significance level of 0.05 as used for the primary endpoint will be used for the secondary endpoints.

All secondary endpoints OS, PP, CYTOC and SSE will be tested sequentially two times, in case the previous endpoint in the hierarchical order was significant. The first test for statistical significance will occur at the time of the MFS analysis and the final test for statistical significance will occur when approximately 240 OS events have been observed.

A rho-family spending function with parameter  $\rho=10$  will be used for OS, time to pain progression, time to cytotoxic chemotherapy and time to first SSE to determine the two stopping boundaries for efficacy at the interim and final analyses. The OS information fraction will be used for determining the alpha spending and significance threshold also for the other secondary endpoints at the interim analysis. For the final analysis the remaining alpha available and the actually observed numbers of events at interim and final for each endpoint will be used to determine the significance thresholds of secondary endpoints.

This rho spending function is slightly more conservative at the first test compared to the O'Brien-Fleming spending function and assigns slightly more alpha at the second test compared to the O'Brien-Fleming spending function. This choice is motivated by the low likelihood to achieve a significant result for the hierarchically first secondary endpoint OS at the first test for both spending functions.

The significance boundaries will be calculated with the EAST software package based on number of events actually observed in the analyzed data sets.

As an example for the planned sequential testing of the secondary endpoint OS, the table shows calculated alpha significance levels ( $\alpha$ ) and standard normal significance thresholds ( $z$ ), assuming numbers of OS events of 140 at interim and 240 at final analysis. See Table 5 for details.

**Table 5: Example for calculated  $\alpha$  significance levels and standard normal thresholds (z) for OS**

	O'Brien-Fleming		Rho family, rho=10	
CCI				

The schema of testing the secondary endpoints is illustrated in Table 6 to Table 8.

**Table 6: Interim analysis for significance; number of OS events and standard normal thresholds are illustrating the example from Table 5**

	140 OS events
	Interim analysis
OS interim dataset	test at z1
	if positive 
PP interim dataset	test at z1
	if positive 
CYTOC interim dataset	test at z1
	if positive 
SSE interim dataset	test at z1

**Table 7: Final Analysis for significance, scenario 1; number of OS events and standard normal thresholds are illustrating the example from Table 5**

Assuming OS interim analysis was not positive:

		240 OS events
		Final analysis
OS final dataset	OS interim not positive 	test at z2
		if positive 
PP interim dataset*		test at z2
		if positive 
CYTOC final dataset		test at z2
		if positive 
SSE final dataset		test at z2

\*PP is a more subjective endpoint, therefore an analysis of PP which includes a large portion of data collected under open-label conditions is not considered meaningful. In case PP would be tested in the final analysis, the interim dataset would be used also for this test procedure.

**Table 8: Final analysis for significance, scenario 2; number of OS events and standard normal thresholds are illustrating the example from Table 5**

Assuming OS interim analysis was positive and PP interim analysis was not positive:

		240 OS events
		final analysis
OS final dataset	OS interim was positive	no test
PP interim dataset*	PPR interim not positive 	test at z2
		if positive 

CYTOC final dataset		test at z2
		if positive 
SSE final dataset		test at z2

In further scenarios where in the interim analysis after OS also PP was positive or where in the interim analysis after OS and after PP also CYTOC was positive, accordingly modified testing sequences would be applied.

The above testing schema is following the testing strategy 2 which is discussed in the publication of Hung et al. [10].

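### If OS passes at the MFS analysis, time to pain progression faces two thresholds on one unchanged dataset, so its claim can be delayed with no gain in error control

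*SAP*

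**What the plan says.** SAP v4.2 section 6.2.2 tests each secondary endpoint only if the one before it was significant. On the level it says: "The same overall two-sided significance level of 0.05 as used for the primary endpoint will be used for the secondary endpoints". Rho-family spending with rho=10 applies to all four endpoints. At the MFS analysis the threshold does not depend on an endpoint's own maturity: "The OS information fraction will be used for determining the alpha spending and significance threshold also for the other secondary endpoints at the interim analysis". At the final analysis, "the actually observed numbers of events at interim and final for each endpoint will be used to determine the significance thresholds of secondary endpoints", together with the alpha that remains.

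The tables in that section then set out the paths:

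- **Table 6 (MFS analysis).** OS at z1. If positive, PP on the interim dataset at z1, then chemotherapy and SSE at z1.
- **Table 7 (OS not positive at the interim).** At the final analysis OS at z2, then PP at z2, still on the interim dataset. The footnote gives the reason: PP is subjective and much of the later data would be open-label. It then states "In case PP would be tested in the final analysis, the interim dataset would be used also for this test procedure".
- **Table 8.** "Assuming OS interim analysis was positive and PP interim analysis was not positive". PP is tested at z2 on the interim dataset, then chemotherapy and SSE at z2 on the final datasets.

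**The concern.** An interim threshold makes sense when more data will come. For PP none will come, because the SAP closes the PP dataset at the MFS analysis. Where OS has passed and PP is tested there, PP data that are already complete are held to a threshold derived from how incomplete the OS data are. The footnote justifies leaving out open-label PP data. It does not explain why the closed dataset should first face z1. The stated motive for rho=10 concerns OS alone.

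Two things are at stake. A PP result between the thresholds changes status later only because more deaths have accrued, which is awkward to explain in a report or label. And while PP waits, chemotherapy and SSE lose their look at the MFS analysis. Their only test then uses later data, which SAP section 6.2.2.1 says crossover to open-label darolutamide may dilute.

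**Working it through.** **Inputs from the SAP.** Overall two-sided alpha 0.05; rho=10; illustrative OS counts, "assuming numbers of OS events of 140 at interim and 240 at final analysis"; 2:1 randomisation.

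**Assumptions.** The documents give no OS effect, PP effect or PP event count. I use OS hazard ratios of 0.75, 0.70, 0.65 and 0.60, and an expected PP Z of 2.5 to 3.0. Table 5's thresholds are redacted, so z1 and z2 below are reconstructions.

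**Thresholds.**
- OS information fraction: 140/240 = 0.5833.
- Alpha at the first test: 0.05 × 0.5833^10 = 0.05 × 0.004562 = 0.000228, so z1 = 3.686.
- For OS, with correlation sqrt(0.5833) between looks, z2 = 1.960 (nominal p 0.04999). Total alpha is 0.0500, matching the SAP's overall level.
- For PP the two looks share all their data, so the correlation is 1 and P(reject) = P(|Z| > min(z1, z2)). Setting this to 0.05 gives z2 = 1.960. The z1 test uses no alpha that the z2 test does not already contain, so withholding the claim until later saves nothing.

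**The gap.** A PP statistic with 1.96 < |Z| < 3.69 (nominal p from about 0.0002 to 0.05) fails in Table 6 and passes in Table 8.

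- Expected Z 2.5: Φ(1.186) − Φ(−0.540) = 0.588.
- Expected Z 3.0: Φ(0.686) − Φ(−1.040) = 0.604.

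Put in terms of power: if PP has 80%, 90% or 95% power at 1.96, its chance of passing z1 is 19%, 33% or 47%.

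**How often PP reaches z1.** OS must first cross 3.686 at 140 deaths: P = Φ(sqrt(140 × 2/9) × |ln HR| − 3.686), with sqrt(140 × 2/9) = 5.578.

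| Assumed OS HR | OS passes at interim | × 0.588 to 0.604 |
|---|---|---|
| 0.75 | 0.019 | about 1% |
| 0.70 | 0.045 | about 3% |
| 0.65 | 0.100 | about 6% |
| 0.60 | 0.201 | about 12% |

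The last column treats the OS and PP statistics as independent.

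**Error rate of a single PP test.** One PP test at 1.96, made as soon as OS is significant, was simulated with PP null, OS drift 0 to 8 and OS–PP correlation 0, 0.5 and 0.9 (4 million runs per setting). The largest PP false-positive rate was 0.0500, the same as under the current scheme.

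**What chemotherapy gains.** It would still need |Z| > 3.686 at the MFS analysis. With the same expected Z of 2.5 to 3.0, that has probability 1 − Φ(1.186) = 0.12 to 1 − Φ(0.686) = 0.25.

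**The case against.** The strongest reply is that the path the SAP expects already does what is wanted. Section 6.2.2 regards OS passing at the first test as unlikely. If OS does not pass, Table 7 tests PP once, on the interim dataset, at z2. The issue is confined to Table 8. That stands, and it limits the size of the point.

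The reply can add that the closed dataset has a sound reason, and that a common boundary across the hierarchy is a prespecified choice attributed to a published strategy. That also stands, but it gives no benefit from holding PP to z1.

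It is also fair that later data contain more chemotherapy and skeletal events, that the open-label offer depends on the sponsor's benefit-risk judgement, and that releasing PP early still leaves chemotherapy and SSE facing z1. The harm to those endpoints is therefore modest.

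Four stronger readings are tempting, and the documents do not support them:

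- *PP must clear both thresholds.* Either is enough; Table 8 applies z2 because z1 was missed.
- *Chemotherapy and SSE are blocked for good.* If PP passes z2, both can still be tested in order at the final analysis.
- *Testing PP twice inflates type I error.* With identical data the second test contains the first, and the level stays at 0.05.
- *The final-boundary rule fails because PP has equal event counts at both looks.* With correlation 1 the boundary is well defined and equals 1.960.

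**Conclusion.** The point holds as one of coherence and efficiency, not validity. When OS is positive at the interim and PP is not, the SAP applies z1 and then z2 to one unchanged PP statistic. A result with nominal p between about 0.0002 and 0.05 is first not significant and later significant. The consequences are a delayed PP claim and no interim look for chemotherapy and SSE.

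On the stated assumptions OS passes at the interim in about 2% to 20% of trials. About 59% to 60% of those fall in the gap, so about 1% to 12% of all trials are affected. The upper end needs an OS hazard ratio of 0.60, stronger than the 0.65 assumed for MFS before dilution, while protocol section 1.6.1 expects that not all of the MFS benefit will carry over to the secondary endpoints. The lower part of the range is therefore more plausible. The thresholds, and the interval of 100 deaths between looks (240 − 140), rest on the SAP's illustrative counts and would move with the observed ones.

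**What to change.** In SAP section 6.2.2 and Tables 6 to 8:

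1. Test PP once, on the interim dataset, at the full two-sided 0.05 (|Z| > 1.96), as soon as OS is significant, whether at the MFS or the final analysis.
2. Delete the repeat PP test in Table 8.
3. Take PP out of the rho=10 spending and out of the rule that sets interim thresholds from the OS information fraction.
4. Keep z1 and z2 for OS, chemotherapy and SSE.

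There is no alpha cost. In a fixed sequence a familywise error requires rejecting the first true null hypothesis, and each endpoint's procedure remains level 0.05. The eventual PP verdict is essentially unchanged; it comes earlier when OS passes at the interim. No new data are needed, only edits to the tables and the accompanying text. The gain for chemotherapy and SSE is limited, because both would still have to pass z1 at the MFS analysis, and the revised text should say so.

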### 6.2.2.1 Overall survival (OS)

OS is defined as time from randomization to death due to any cause. OS of patients not known to have died will be censored at their last date of being known to be alive or at the database cutoff date, whichever comes first. OS will be analyzed on the FAS population.

If a patient died and the date of death is completely or partially missing, but there is an AE with the outcome as ‘Death’, the date of death will be replaced by the end date of the AE.

If the complete date of death is not known, but the year and month are available and there is no AE with outcome as ‘Death’, Day 15 of the month will be used for the calculation of the time to death.

Table 9 will be used for calculating the OS; time to death = End Date – Date of Randomization+1.

**Table 9: Censoring Rules for OS**

Situation	End Date on or prior to cut-off date	Censored
Death during study	Date of death	No
Patient still alive at data cut-off	Date of data cut-off	Yes
Patient lost to follow-up before data cut-off	Date last known to be alive	Yes
Patient lost to follow-up without contact after randomization	Date of randomization	Yes

This endpoint is selected from the ADTTE dataset using variable PARAMCD equal to ‘DEATH’.

The Last Known Alive Date (LKAD) is derived from the main data sources. The last available date across all selected data panels listed below will be picked as the LKAD by patient. Information from selected data, i.e. visit dates, exposure information, demographics, laboratory measurements, tumor assessment dates, MFS dates, SSE dates, survival status date, and disposition events or follow up assessments will be used to determine survival status. Within all the dates from the selected data panels, identify the latest available date as the LKAD for each patient.

A log rank test stratified by stratification factor of PSADT ( $\leq 6$  vs.  $>6$  months) and use of osteoclast-targeted therapy (yes vs. no) at randomization (i.e. from IVRS) will be used to compare the darolutamide treated and placebo groups.

The hazard ratio as well as its 95% CI will be presented based on fitting a Cox regression model with treatment as factor and stratified by PSADT ( $\leq 6$  vs.  $>6$  months) and use of osteoclast-targeted therapy (yes vs. no) at randomization.

Kaplan-Meier survival curves (product-limit estimates) will be presented by treatment arm (including display of numbers at risk at various time points). The Kaplan-Meier estimate of the median survival time and first and third quartiles will be presented with 95% CI. Greenwood's formula will be used for the standard error of the Kaplan-Meier estimate in the calculation of these confidence limits.

The number and percentage of patients in each treatment group who have died will be summarized at yearly time points along with the number and percentage of censored patients. Summaries by cause of death will be provided too.

Descriptive statistics of survival follow-up time will be calculated by treatment arm and total. Follow-up time (days) is the time to death as described for the OS endpoint for censored and uncensored patients.

Once the study results are available, and if they support a positive benefit/risk assessment for darolutamide in the study by judgment of the Sponsor (considering feedback from the study steering committee and/or health authorities), those patients who are on study treatment (darolutamide or placebo) will be offered the opportunity to receive darolutamide through open-label treatment in this study. This may dilute the effect size for the secondary endpoints as the placebo arm outcomes will become more similar to the darolutamide arm outcomes. The amount of this bias can be approximately assessed by established crossover adjustment methods like Rank-Preserving Structural Failure Time (RPSFT) [7] or Iterative Parametric Estimation (IPE) [5]. These methods construct a placebo arm Kaplan-Meier curve which is expected to resemble the Kaplan-Meier (KM) curve which would be observed if placebo to darolutamide crossover would not had occurred. The data of the second analysis of OS will be analyzed in addition with the RPSFT and IPE methods. Only the unadjusted OS data will be used for testing for a statistically significant treatment effect.

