### **3.1 Determination of Sample Size**

Several clinical publications were used as basis for the sample size calculation. The median MFS for placebo is based on denosumab phase III study results [8] at the time the ARAMIS protocol was designed, no data were available on the expected treatment effect size for androgen-receptor inhibitors in high-risk nmCRPC patients. Data published in 2016 and recently published data from SPARTAN and PROSPER phase III trials indicate, that the treatment effect of the class of novel androgen receptor inhibitors (enzalutamide, apalutamide) is stronger than initially assumed

Given the results from PROSPER and SPARTAN, the initial assumption for the treatment effect size of a hazard ratio of 0.75 was considered as too conservative.

All patients had to have an independent evaluation of radiological images for no baseline metastases at baseline to be eligible for randomization. However, for the central efficacy review, the baseline scans were again reviewed. During this review some patients were identified with metastases at baseline; to calculate sample size these patients are considered as having a MFS event on the date of randomization.

The number of events has been adjusted to account for the non-informative character of baseline metastases events and the dilution impact to the estimated MFS hazard ratio.

The assumptions used in determining the sample size for this study are as follows:

- Overall 2-sided type I error rate: 0.05,
- Assumed hazard ratio of 0.65,

- Accounting for 5% of the patients with baseline metastasis, diluted hazard ratio of 0.71,
- Randomization ratio: 2:1
- Statistical power at the final analysis: 91%,
- Median MFS for placebo: 25 months,

385 MFS events will provide approximately 91% power to detect a statistically significant difference in MFS times, with a two-sided log-rank test with a 0.05 level of significance. With 40 months accrual time and a dropout rate of 40%, the study will require approximately 1500 patients (1000 darolutamide patients, 500 placebo patients) to achieve the targeted 385 MFS events. The MFS analysis will be performed when the targeted number of approximately 385 MFS events has been observed.

This sample size calculation was performed with a simulation based algorithm.

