Sample code to produce stratified log rank test:

```
proc lifetest data=data;
  time prog_time*cnsr(1);
  strata psa_double ot_therapy / group=treat test=(logrank);
run;
```

Where:

*prog\_time* contains metastasis free survival time for the patient, *cnsr* contains a value of one for censored records and zero otherwise, *psa\_double* contains PSA doubling time category at randomization, *ot\_therapy* contains category for osteoclast-targeted therapy use at randomization, *treat* contains assigned treatment group.

The hazard ratio as well as its 95% confidence interval (CI) will be presented based on fitting a Cox regression model with treatment as factor and stratified by PSA doubling time ( $\leq 6$  vs.  $> 6$  months) and use of osteoclast-targeted therapy (yes vs. no) at randomization.

Sample code to produce hazard ratio:

```
proc phreg data=data;
  model prog_time *cnsr(1) = trtpn;
  strata psa_double ot_therapy / missing;
run;
```

Where:

*prog\_time* contains metastasis free survival time for the patient, *cnsr* contains a value of one for censored records and zero otherwise, *psa\_double* contains PSA doubling time category at randomization, *ot\_therapy* contains category for osteoclast-targeted therapy use at randomization, *treat* contains assigned treatment group.

The Kaplan-Meier estimate of the median survival time and first and third quartiles will be presented with 95% CI. The survival curves will also be plotted. 4, 8, 12, months MFS rate time-points will also be provided with 95% CI. Greenwood's formula will be used for the standard error of the Kaplan-Meier estimate in the calculation of these confidence limits. The number and percentage of patients in each treatment group who have progressed or died at 4, 8, 12 months will be summarized along with the number and percentage of censored patients.

Sample code to produce Kaplan Meier curves:

```
proc lifetest data=data method=km outsurv=outsurv;  
time prog_time *cnsr(1);  
strata treat;  
run;
```

Where:

*Prog\_time* contains metastasis free survival time for the patient, *cnsr* contains a value of one for censored records and zero otherwise, *treat* contains assigned treatment group.

If the complete date of the scan is not known, but the year and month are available, Day 15 of the month will be used for the calculation.

If the complete date of the death is not known, but the year and month are available, Day 15 of the month will be used for the calculation.

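### Overall survival gets crude yearly death percentages but no Kaplan-Meier rates at fixed times, and its follow-up time ends at death, so early absolute mortality and data maturity are understated

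*SAP*

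**What the plan says.** SAP v4.2 section 6.2.2.1 gives these absolute outputs for OS:

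- Kaplan-Meier curves by arm, with numbers at risk.
- Kaplan-Meier median and quartiles with 95% intervals, using Greenwood's standard error.
- A fixed-time summary: "The number and percentage of patients in each treatment group who have died will be summarized at yearly time points". The same sentence adds the number and percentage censored.
- Survival follow-up by arm and in total: "Follow-up time (days) is the time to death as described for the OS endpoint for censored and uncensored patients". A death therefore ends a man's follow-up.

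Other endpoints get more at fixed times. For metastasis-free survival (MFS), section 6.2.1.1 has "4, 8, 12, months MFS rate time-points will also be provided with 95% CI", in addition to a crude summary of the same kind as for OS. Section 6.2.3.1 plans fixed-time rates for progression-free survival, and sections 6.2.3.9.2 and 6.2.3.9.4 plan deterioration-free rates at 12, 24 and 36 months for two quality-of-life endpoints.

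OS is first in the secondary hierarchy (section 6.2.2). Its final test is due at about 240 deaths, and the worked example puts 140 deaths at the interim. Section 3.1 sets the entry pattern: "With 40 months accrual time and a dropout rate of 40"%, with about 1500 patients.

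**The concern.** A crude percentage dead by year 3 keeps every randomised man in the denominator, including those whom the cut-off leaves with less than three years of possible follow-up. They are counted as not dead. The result is not an estimate of 3-year mortality, and it falls short by more the earlier the cut-off.

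This would matter little if the Kaplan-Meier quantiles carried the absolute message. With so few deaths they mostly cannot, so the crude percentages would become the main tabulated figures for absolute survival. They would also compress the absolute difference between arms.

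The follow-up summary has a related flaw. Because a death shortens follow-up, the figure mixes data maturity with mortality, and the arm with more deaths looks less well followed.

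**Working it through.** **Inputs from the documents.** Accrual 40 months, about 1500 men, 2:1 allocation (SAP 3.1); 140 deaths at interim as an example, about 240 at final (SAP 6.2.2); study start Q3 2014, completion 2020 (Protocol 8.14).

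**The plan's own figure.** The documents state no OS hazard, OS rate or OS cut-off date, so there is no OS figure to reproduce. As a check on the design inputs, the MFS power with 385 events and diluted hazard ratio 0.71 by Freedman's formula is Φ(√(385×2) × 0.29/2.42 − 1.96) = Φ(1.365) = 91.4%, against the stated 91%.

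**Assumptions (mine).** Uniform accrual, exponential OS, OS hazard ratio 0.7, no loss to survival follow-up, cut-off T months after first entry.

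**Step 1: match the hazard to the death count.** The probability of an observed death is p(λ,T) = 1 − [exp(−λ(T−40)) − exp(−λT)]/(40λ). Solve 500·p(λ,T) + 1000·p(0.7λ,T) = 140 or 240 for the placebo hazard λ. At T=48 with 140 deaths, λ = 0.004419 per month (57.6 placebo + 82.4 darolutamide deaths).

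The 44-month placebo median that Protocol 1.1 quotes from another trial cannot be used here. It would bring 240 deaths by about month 31 to 34, before accrual ends.

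**Step 2: true and crude 3-year mortality.** True = 1 − exp(−36λ). Crude = the average of 1 − exp(−λ·min(f,36)) over potential follow-up f, uniform from T−40 to T. At T=48, placebo:

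- True: 1 − exp(−0.1591) = 14.71%.
- Men with f ≥ 36 are 12/40 = 30% and contribute 0.30 × 14.71% = 4.41 points.
- Men with f from 8 to 36 contribute [28 − (0.96527 − 0.85293)/0.004419]/40 = 6.44 points.
- Crude: 10.86%, which is 26% too low.

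Darolutamide at T=48: true 10.54%, crude 7.75%, also about 26% too low. The absolute difference shrinks from 4.17 to 3.11 points.

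| Deaths | Cut-off (month) | True, placebo | Crude, placebo | Understated by |
|---|---|---|---|---|
| 140 | 42 | 18.4% | 11.3% | 39% |
| 140 | 48 | 14.7% | 10.9% | 26% |
| 140 | 52 | 13.0% | 10.5% | 19% |
| 240 | 54 | 20.9% | 17.6% | 16% |
| 240 | 60 | 18.0% | 16.5% | 8% |
| 240 | 66 | 15.8% | 15.3% | 3% |
| 240 | 72 | 14.1% | 14.0% | 1% |

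With 5% survival loss per 3 years the understatement is 28% at month 48, 10% at month 60 and 6% at month 66.

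**Step 3: are the quantiles reachable?** First quartile = ln(4/3)/λ, median = ln 2/λ. At T=48 the first quartile is 65 months on placebo and 93 on darolutamide, both beyond the cut-off. Over interim cut-offs at months 42 to 52 it is 51 to 75 months on placebo and 73 to 107 on darolutamide. At a final at month 60, the placebo first quartile (52 months) is within reach, the darolutamide one (75) is not, and the medians are 126 and 180 months.

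**Step 4: follow-up.** The median by the SAP definition solves ((T−x)/40)·exp(−λx) = 0.5. Median potential follow-up is T−20.

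| Cut-off (month) | Placebo | Darolutamide | Potential | Gap between arms |
|---|---|---|---|---|
| 48 | 25.6 | 26.3 | 28.0 | 0.7 |
| 60 | 35.7 | 37.0 | 40.0 | 1.3 |
| 66 | 41.6 | 42.9 | 46.0 | 1.3 |

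With an OS hazard ratio of 1 the gap vanishes, but both arms are still understated (26.1 against 28.0 months at month 48).

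**The case against.** The strongest reply is that little is hidden. The yearly summary shows the censored beside the dead, so its incompleteness is visible, and the SAP does not call the percentages mortality estimates. The planned curves with numbers at risk let a reader take censoring-adjusted survival off the plot. MFS has the same kind of crude companion table. The follow-up definition is stated openly. At a late final cut-off the bias is a few per cent. All of this stands, and it limits the size of the point. It does not remove it: the censored count signals the problem without correcting the percentage, and a value read off a curve has no confidence interval.

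Three stronger readings are tempting, and the documents do not support them.

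- **That 3-year mortality is understated by more than two-fifths.** This needs a cut-off at the end of accrual (41% at month 40, with a 44-month median), or the 40% dropout applied to survival at an early cut-off (48% at month 42). That dropout is given for the MFS sample size, whereas the Protocol continues survival follow-up after treatment stops and adds a survival sweep before OS analyses. SAP v4.2, dated 20 September 2018, still describes the analysis as to come, about 48 to 51 months after a Q3 2014 start.
- **That the treatment comparison is biased.** The relative understatement is about equal in both arms, and the stratified log-rank test and Cox model do not use these percentages.
- **That staggered entry makes follow-up look unequal.** The gap between arms comes from a difference in deaths.

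**Conclusion.** The point holds as a reporting weakness in absolute OS results, not as a flaw in inference. It matters chiefly for the interim OS report, where the crude 3-year percentage would be too low by about 19 to 39% at months 42 to 52. At a month-54 final the figure is 16%, and at months 60 to 72 it is 1 to 8%. Survival loss would add to this. The follow-up definition understates potential follow-up by about 2 to 4 months and opens a gap of about 1 month between arms when deaths differ.

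The direction follows from the definitions and from staggered entry. The sizes rest on the assumed uniform accrual, exponential OS, hazard ratio 0.7 and cut-off months, none of which the documents fix for OS.

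**What to change.** In SAP section 6.2.2.1:

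1. Add Kaplan-Meier OS probabilities at 1, 2, 3 and later years for each arm, with 95% intervals by Greenwood's formula. Keep the crude dead and censored counts as a companion table, as for MFS.
2. Report median OS follow-up by reverse Kaplan-Meier (deaths censored, censorings as events), per arm and overall.

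The cost is one sentence each and a few lines in the Kaplan-Meier program already planned. No new data are needed, and no test or alpha allocation changes.
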